## EXCLUDED MEDICATIONS AND FOODS FOR PATIENTS RECEIVING REGORAFENIB

Strong CYP3A4 Inhibitors	Strong CYP3A4 Inducers	Strong UGT1A9 Inhibitors
Boceprevir	Carbamazepine	Mefenamic acid
Clarithromycin	Phenytoin	diflunisal
Cobicistat	Rifampin	Niflumic acid
Conivaptan	St. John's Wort	
Grapefruit, grapefruit juice	Phenobarbital	
Indinavir		
Itraconazole		
Ketoconazole		
Lopinavir		
Nefazodone		
Nelfinavir		
Posaconazole		
Ritonavir		
Saquinavir		
Telaprevir		
Telithromycin		
Voriconazole		

Abbreviations: CYP3A4 = cytochrome P450 3A4.

This list is not intended to be exhaustive. A similar restriction will apply to other drugs that are known to strongly modulate CYP3A4 via inhibition or induction or are strong inhibitors of UGT1A9; appropriate medical judgement is required. Please contact Blueprint Medicines with any queries you have on this issue.

**18.4 Appendix 4****MEDICATIONS TO BE USED WITH CAUTION WITH AVAPRITINIB**

CYP3A4 Substrates	CYP2C9 Substrates	BCRP Substrates	Moderate CYP3A4 Inhibitors
Alfentanil	Warfarin	Rosuvastatin	Erythromycin
Cyclosporine		Methotrexate	Fluconazole
Dihydroergotamine		Lapatinib	Crizotinib
Ergotamine			Dronedarone
Fentanyl			Imatinib
Midazolam			Diltiazem
Pimozide			
Quinidine			
Simvastatin			
Sirolimus			
Tacrolimus			
Terfenadine			

Abbreviations: BCRP = Breast Cancer Resistance Protein; CYP3A4 = Cytochrome P450 3A4; CYP2C9 = cytochrome P450 2C9

This list is not intended to be exhaustive. A similar restriction will apply to other drugs that are sensitive substrates of CYP3A4, CYP2C9, or BCRP, and moderate inhibitors of CYP3A4; appropriate medical judgement is required. Please contact Blueprint Medicines with any queries you have on this issue.

**MEDICATIONS TO BE USED WITH CAUTION WITH  
REGORAFENIB**

BCRP Substrates
Methotrexate
Fluvastatin
Atorvastatin

Abbreviations: BCRP = Breast Cancer Resistance Protein.

**18.5 Appendix 5****EASTERN COOPERATIVE ONCOLOGY GROUP PERFORMANCE STATUS**

Grade	Symptomatology
0	Fully active, able to carry on all pre-disease performance without restriction
1	Restricted in physically strenuous activity but ambulatory and able to carry out work of a light or sedentary nature, eg, light house work, office work
2	Ambulatory and capable of all self-care but unable to carry out any work activities. Up and about more than 50% of waking hours
3	Capable of only limited self-care, confined to bed or chair more than 50% of waking hours
4	Completely disabled. Cannot carry on any self-care. Totally confined to bed or chair
5	Dead

Source: ([Oken et al, 1982](#)).

**18.6 Appendix 6****MODIFICATIONS TO RESPONSE EVALUATION CRITERIA IN  
SOLID TUMORS VERSION 1.1 (MRECIST 1.1), FOR PATIENTS  
WITH GIST**

1. No lymph nodes to be chosen as target lesions. Enlarged lymph nodes are to be followed up as non-target lesions.
2. No bone lesions to be chosen as target lesions.
3. Fluorodeoxyglucose positron emission tomography (FDG-PET) is not acceptable for radiological assessment.
4. A progressively growing new tumor nodule within a pre-existing tumor mass must meet the following criteria in order to be regarded as unequivocal evidence of progressive disease:
  - a. The lesion must be  $\geq 2$  cm in size and definitely be a new active GIST lesions (eg, enhanced with contrast or other criteria to rule out artifact); or
  - b. The lesion must be expanding on at least 2 sequential imaging studies.

Source: ([Demetri et al, 2013a](#))

[figure not shown]
**18.7 Appendix 7**

[figure not shown]
[Redacted]

[Redacted]

[Redacted]

**18.8 Appendix 8**

18.9

[Redacted]

[Redacted]

[Redacted]

[Redacted]

\_\_\_\_\_

[Redacted]

\_\_\_\_\_

[Redacted]

[Redacted]

[Redacted]

[Redacted]

[Redacted]

[Redacted]

[figure not shown]
[Redacted]

[Redacted]

[figure not shown]
[Redacted]

[figure not shown]
[Redacted]

**18.10 Appendix 10**

[figure not shown]

**18.11 Appendix 11**

[figure not shown]

[figure not shown]

[figure not shown]

[figure not shown]

**Avapritinib**  
**Statistical Analysis Plan Study BLU-285-1303**

**LIST OF ABBREVIATIONS AND DEFINITIONS OF TERMS**

Abbreviation	Term
AE	Adverse event
AESI	Adverse event of special interest
ANC	Absolute neutrophil count
ATC	Anatomical therapeutic chemical
β-hCG	Beta human chorionic gonadotropin
BMI	Body mass index
BP	Blood pressure
BSC	Best supportive care
C3D1	Cycle 3 Day 1
CBR	Clinical benefit rate
CI	Confidence interval
CR	Complete response
CS	Clinically significant
CSR	Clinical study report
CT	Computed tomography
CTCAE	Common Terminology Criteria for Adverse Events
ctDNA	Circulating tumor deoxyribonucleic acid
CXDX	Cycle X Day X
D842V	Aspartic acid to valine at amino acid 842
DCR	Disease control rate
DE	Dose escalation
DOR	Duration of response
ECG	Electrocardiogram
ECOG PS	Eastern Cooperative Oncology Group Performance Status
EORTC-QLQ-C30	European Organisation for Research and Treatment of Cancer Quality of Life
EQ-5D-5L	EuroQol 5 Dimension
eCRF	Electronic case report form
EMA	European Medicines Agency
EOT	End-of-treatment
FDA	Food and Drug Administration
GIST	Gastrointestinal stromal tumors
IDMC	Independent Data Monitoring Committee
ITT	Intent-to-Treat
IV	Intravenous
IWRS	Interactive web response system
KIT	V-Kit Hardy-Zuckerman 4 feline sarcoma viral oncogene homolog
KM	Kaplan-Meier
MAF	Mutant allele fractions
MedDRA	Medical Dictionary for Regulatory Activities
MRI	Magnetic resonance imaging

**Avapritinib**  
**Statistical Analysis Plan Study BLU-285-1303**

Abbreviation	Term
mRECIST 1.1	Modified Response Evaluation Criteria in Solid Tumors version 1.1
NCI	National Cancer Institute
NCS	Not clinically significant
NE	Not evaluable
ORR	Overall response rate
OS	Overall survival
PD	Progressive Disease
PFS	Progression free survival
PDGFRA	Platelet-derived growth factor receptor alpha
PK	Pharmacokinetic
PR	Partial response
PRO	Patient reported outcome
PT	Preferred term
QD	Once daily
QoL	Quality of life
QTcF	QT interval corrected using Fridericia's formula
RDI	Relative dose intensity
RE	Response-evaluable
R/R	Relapsed or refractory
RPSFT	Rank preserving structural failure time
SAE	Serious adverse event
SAP	Statistical analysis plan
SD	Stable disease
SOC	System organ class
StdDev	Standard deviation
TEAE	Treatment-emergent adverse event
TKI	Tyrosine kinase inhibitor
TNM	Tumor/lymph nodes/metastasis
TTR	Time to response
ULN	Upper limit of normal
US	United States (of America)
VAS	Visual analog scale
WHO	World Health Organization

**Avapritinib**  
**Statistical Analysis Plan Study BLU-285-1303**

**1. INTRODUCTION**

This statistical analysis plan (SAP) describes the statistical analyses and data presentations to be performed for Blueprint Medicines, Protocol No. BLU-285-1303 (amendment 3 dated 20 JUN 2019) ‘An International, Multicenter, Open-label, Randomized, Phase 3 Study of Avapritinib (BLU-285) vs Regorafenib in Patients with Locally Advanced Unresectable or Metastatic Gastrointestinal Stromal Tumor (GIST)’. It contains definitions of analysis populations, derived variables, and statistical methods for the analysis of efficacy and safety. It is to ensure that the data listings, summary tables, and figures which will be produced, and the statistical methodologies that will be used, are complete and appropriate to allow valid conclusions regarding the study objectives.

The SAP will be finalized and approved prior to the clinical database lock for the final analysis, when approximately 264 progression free survival (PFS) events are reached. The analyses of safety, efficacy and pharmacokinetics will include all data collected in the database through the data cutoff date.

A follow-up analysis for overall survival will be conducted when approximately 264 deaths have been observed. Additional data collected after the database lock from the primary analysis of the study will be prepared as an addendum to the study report per regulatory or scientific need.

Selected analyses from this SAP will be performed for the Independent Data Monitoring Committee (IDMC) to review accumulated data from the study. Further details are described separately in the IDMC Charter.

Analysis of pharmacokinetics (PK) is outside the scope of this SAP and will be addressed separately.

**Avapritinib**  
**Statistical Analysis Plan Study BLU-285-1303**

**1.1 Study Design**

This is an open-label, randomized, Phase 3 study in patients with locally advanced unresectable or metastatic GIST previously treated with imatinib and 1 or 2 other tyrosine kinase inhibitors (TKIs).

All study visits are intended to be conducted on an outpatient basis. After provision of written informed consent, patients will be evaluated for study eligibility during the screening period within 4 weeks (28 days) before study drug administration on Cycle 1 Day 1 (C1D1). During the screening period, eligibility will be confirmed; management of baseline concomitant conditions will be recorded and stabilized; baseline symptoms will be assessed; hematology, blood chemistry, mutation status, brain imaging (computed tomography (CT) scan or magnetic resonance imaging (MRI)), and baseline tumor assessments (CT scan or MRI) will be performed.

[figure not shown]
Approximately 460 patients are to be randomly assigned, in a 1:1 ratio, to 1 of 2 treatment arms: Arm A (avapritinib) or Arm B (regorafenib) stratified by TKI treatment (third versus fourth), geographic region (Asia versus rest of the world), and PDGFRA D842V mutation status measured in ctDNA or a tumor sample (PDGFRA D842V mutation present versus absent). PDGFRA D842V mutation present is defined if a PDGFRA D842V mutation is detected per local or/and central testing. At least 70% of the patients enrolled should be receiving the study drug as their third TKI treatment for GIST.

Patients randomized to Arm A will receive avapritinib 300 mg orally (PO) once daily (QD) with the option to escalate to 400 mg PO QD at the Investigator's discretion (the escalation option was removed in protocol amendment 3), if specific criteria are met as described in the protocol. Patients randomized to Arm B will receive regorafenib 160 mg PO QD for 3 weeks out of every 4 week (28 days) cycle (i.e., 3 weeks on/1 week off).

Patients who experience disease progression on avapritinib as determined by central radiology may be offered the opportunity to continue treatment with avapritinib if there is no clinical evidence of disease progression or laboratory abnormalities attributable to disease progression, no rapid progression of disease or a progressive tumor requiring urgent alternative medical intervention at critical anatomical sites, and no decline in Eastern Cooperative Oncology Group Performance Status (ECOG PS). Patients who experience disease progression on regorafenib, as determined by central radiology, may be offered the opportunity to cross over to avapritinib.

**Avapritinib**  
**Statistical Analysis Plan Study BLU-285-1303**

**Figure 1: Study Schematic**

Abbreviations: GIST = gastrointestinal stromal tumor; N = number of patients; R = randomized; TKI = tyrosine kinase inhibitor.

**Avapritinib**  
**Statistical Analysis Plan Study BLU-285-1303**

**1.2 Study Objectives**

**1.2.1 Primary Objectives**

The primary objective is to demonstrate the efficacy of avapritinib based on PFS as determined by central radiological assessment per mRECIST 1.1 in patients with advanced GIST following 2 or 3 prior TKI therapies, including imatinib, compared to patients treated with regorafenib.

**1.2.2 Secondary Objectives**

[figure not shown]
The key secondary objectives are:

- To evaluate objective response rate (ORR) as determined by central radiological assessment per mRECIST 1.1 in patients with advanced GIST treated with avapritinib compared to patients treated with regorafenib.
- To evaluate overall survival (OS) in patients with advanced GIST treated with avapritinib compared to patients treated with regorafenib.

Additional secondary objectives are:

- To evaluate the European Organisation for Research and Treatment of Cancer Quality of Life (EORTC-QLQ-C30) individual scores in patients with advanced GIST treated with avapritinib compared to patients treated with regorafenib.
- To evaluate the safety and tolerability of avapritinib compared to regorafenib.
- To evaluate objective response rate as assessed by the Investigator per mRECIST 1.1 in patients with advanced GIST treated with avapritinib compared to patients treated with regorafenib.
- To evaluate objective response rate as determined by central radiological assessment per Choi criteria in patients with advanced GIST treated with avapritinib compared to patients treated with regorafenib.
- To evaluate disease control rate (DCR) per mRECIST 1.1 in patients with advanced GIST treated with avapritinib compared to patients treated with regorafenib.
- To evaluate duration of response (DOR) per mRECIST 1.1 in patients with advanced GIST treated with avapritinib compared to patients treated with regorafenib.
- To determine steady state systemic exposure of avapritinib (out of scope for this SAP).
- To assess the patient-reported perception of abdominal pain.

**1.2.3 Exploratory Objectives**

### **1.3 Sample Size Justification**

The sample size calculation was based upon the assumption that the median PFS for regorafenib is approximately 5 months (Demetri 2013). Assuming avapritinib can reduce the risk of PFS events by 33%, i.e., a hazard ratio (HR) of 0.67 (avapritinib compared to regorafenib), a minimum of 264 PFS events are needed to provide 90% power at a 2-sided alpha of 0.05 for the study. With an 18-month accrual period and a 6-month follow-up period, the total sample size needed for the study is approximately 460 patients (230 patients per arm). This sample size takes a 2% dropout rate into consideration and assumes accrual will follow a truncated exponential distribution with a scaled power parameter of -9.

The sample size calculated for the primary endpoint, PFS, is also sufficient to detect a difference in ORR between the two arms. Assuming a null ORR of 5% and an alternative ORR of 15%, a sample size of 460 patients provides approximately 95% power to detect a difference in ORR using a test of two-proportions at a 2-sided alpha of 0.05.

Assuming the same effect size for OS as PFS (HR = 0.67), the same number of events (264) is required to power the OS analysis. The timing of the OS analysis will occur later than the PFS analysis as it will be at such time when 264 deaths occur.

### **1.4 Endpoints**

#### **1.4.1 Primary Efficacy Endpoint**

The primary endpoint is PFS, based on central radiological assessment per mRECIST 1.1, in patients with advanced GIST. Progression-free survival is defined as time from randomization to the earlier of disease progression or death due to any cause.

#### **1.4.2 Secondary Efficacy Endpoints**

The key secondary endpoints are:

- ORR defined as the percentage of patients whose best response is complete response (CR) or partial response (PR) as assessed by central radiology using mRECIST 1.1.
- OS defined as the time from date of randomization to death due to any cause.

[figure not shown]
Additional secondary endpoints include:

## **Avapritinib**

### **Statistical Analysis Plan Study BLU-285-1303**

- All individual EORTC-QLQ-C30 scores, including symptom and function scales, and the global health status score.
- ORR as assessed by Investigator per mRECIST 1.1.
- ORR as assessed by central radiology per Choi criteria.
- DCR is defined as the rate of CR or PR of any duration or stable disease (SD) lasting at least 16 weeks from the date of randomization.
- Duration of response defined as the time from first documentation of tumor response to disease progression or death due to any cause.
- Adverse events, serious AEs (SAEs), and changes in safety laboratory parameters, 12-lead ECG evaluations, and ECOG PS. The intensity of AEs will be assessed by the NCI CTCAE, version 4.03 or 5.0.
- Abdominal pain as measured by a numeric rating scale (0-10).

#### **1.4.3 Exploratory Endpoints**

## **2. POPULATIONS FOR ANALYSIS**

### **2.1 Intent-to-Treat (ITT) Population**

The ITT Population includes all randomized patients, independent of whether they received the study medication or not. All primary efficacy analyses will be based on the ITT Population. All patients in the ITT Population will be analyzed according to the treatment they were randomized to receive.

### **2.2 Safety Population**

The Safety Population includes all patients who have received at least 1 dose of study drug. All patients in the Safety Population will be analyzed according to the treatment actually received.

### **2.3 Per Protocol (PP) Population**

The PP Population includes all patients in the ITT Population who have no major violations of the inclusion/exclusion criteria or other major deviations as specified in the “*Protocol Deviations and Non-Compliance Management Plan*”. Patients who actually receive incorrect treatment compared to what they were randomized to receive will be excluded from the PP Population. The PP Population will be used for selected efficacy analyses as supportive analyses.

### **2.4 Response-Evaluable (RE) Population**

The RE Population is defined as all patients in the ITT Population who received at least 1 dose of avapritinib or regorafenib, have at least 1 target lesion at baseline as determined by central radiology per mRECIST 1.1, and have at least 1 post-baseline disease assessment by central radiology per mRECIST 1.1. Selected efficacy analysis will be performed using the RE Population. Results in this population will be analyzed according to the treatment to which patients were randomized to receive.

### **3. GENERAL STATISTICAL CONSIDERATIONS**

#### **3.1 Randomization, Stratification, and Blinding**

Patients who meet all study eligibility criteria will be randomized by an interactive web response system (IWRS).

The randomization will be stratified by the following 3 variables (stratification factors):

- TKI treatment (third versus fourth)
- Geographic region (Asia versus rest of the world)
- PDGFRA D842V mutation (present versus absent).

If a patient is randomized using incorrect baseline information from the stratification factors, that randomization will be accepted but the analysis will be based on the correct baseline information.

If fewer than 5 patients are in a stratification group of all three factors, that group will be combined with another stratification group. If the PDGFRA D842V is present in fewer than 24 patients overall (i.e., on average, each combination of the other two stratification under each treatment arm contains fewer than 3 patients), then all stratified analyses in this SAP will be based only on TKI treatment and geographic region stratification factors.

To control bias during the study conduct and analyses, and to ensure proper type I error control, patient treatment assignments are blinded to pre-defined study team members (refer to “*Plan for Providing Blinded Data to Biostatistics*” for details). An unblinded team will conduct analyses by treatment, e.g., IDMC until the final database lock, upon which the study team will be unblinded to conduct the primary analysis.

#### **3.2 Data Analysis General Information and Definition**

Summary statistics for continuous variables will include n (non-missing observations), mean, standard deviation (StdDev), minimum, median, and maximum. Summary statistics for categorical variables will be presented in terms of frequencies and percentages. Time to event data will be summarized using the Kaplan-Meier (KM) method, which will include the estimated median with 95% confidence interval (CI) and the 25th and 75th percentiles. All relevant patient data will be included in listings.

##### **3.2.1 Study Drug**

Study drug or study treatment refers to avapritinib or regorafenib.

### 3.2.2 Day 1 and Other Days

**Date of first dose of study drug (or Day 1)** is defined as the day of the first administration of study drug after enrollment. First dose refers to first dose in study unless otherwise specified.

**Date of first dose of study drug during extended study treatment period (or CC1D1)** is defined as the day of the first administration of study drug after cross-over or continuation post disease progression per central radiology.

**Date of last dose of study drug** is defined as the date of last administration of study drug (last dose) in the study. For patients who have not ended treatment and whose last dose date is missing, the cutoff date will be used. The date of last dose of study drug will be calculated separately for the main study treatment period, the extended study treatment period, and both periods combined.

The **extended study treatment period** (or extended study) is defined as any time on or after CC1D1 in the study.

The **main study treatment period** (or main study) is defined as any time before CC1D1 in the study.

**Day -1** is defined as the day before the first administration of study drug in the study (Day 1).

### 3.2.3 Calculations Using Dates

Calculations using dates will adhere to the following conventions:

Study day for a date of interest (TARGET DATE) is calculated as

$$\begin{aligned} \text{STUDY DAY} &= \text{TARGET DATE} - \text{Day 1} + 1 \text{ if TARGET DATE is on or after Day 1;} \\ \text{STUDY DAY} &= \text{TARGET DATE} - \text{Day 1} \text{ otherwise.} \end{aligned}$$

Note that negative study days are reflective of observations obtained during the screening period.

Age (in days) is calculated as

$$\text{AGE} = \text{CONSENT DATE} - \text{BIRTH DATE (DOB)} + 1.$$

Age (in years) is calculated as

$$\begin{aligned} \text{Age (in years)} &= (\text{year of consent}) - (\text{year of DOB}) \text{ if the day of consent} \geq \text{birthday;} \\ \text{Age (in years)} &= (\text{year of consent}) - (\text{year of DOB}) - 1 \text{ otherwise.} \end{aligned}$$

This is equivalent to the following:

$$[(\text{year of consent}) - (\text{year of DOB})] - [(\text{month of consent}) \leq (\text{month of DOB})] + [(\text{month of consent}) = (\text{month of DOB}) \text{ and } (\text{day of consent}) \geq (\text{day of DOB})]$$

**Avapritinib**  
**Statistical Analysis Plan Study BLU-285-1303**

**3.2.4 Duration Derivation**

Unless otherwise specified for a specific panel or variable, duration variables will be derived according to the following rules:

Duration (in days) = [end date – start date +1]

Duration (in weeks) = [end date – start date +1] / 7

Duration (in months) = [end date – start date +1] / 30.4375

Duration (in years) = [end date – start date +1] / 365.25.

Duration variables expressed in units greater than day will be rounded to 1 decimal place.

**3.2.5 Baseline and Rebaseline Values**

Baseline is defined as the last observation prior to first dose of study drug, i.e., the Day 1 pre-dose value or the last available (including unscheduled) value before Day 1 if a Day 1 pre-dose value is unavailable. For summaries using the ITT Population, patients who were randomized but did not receive study drug will be baselined at their last available observation.

Rebaseline is defined as the last observation prior to first dose of avapritinib in the extended study treatment period. For summaries using the ITT Population, patients who signed informed consent to crossover to avapritinib post-disease progression but did not subsequently receive study drug will be re-baselined at their last available observation. Patients who are initially randomized to avapritinib will not be rebaselined for continuation to avapritinib post-disease progression.

**3.2.6 Last Contact**

Last contact or last date known alive is defined as the last non-imputed date of any patient record prior to or on the data cutoff date in the clinical database.

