## **7.9 Survival Follow-up**

After documentation of disease progression by central radiology review, patients or their designated care giver will be contacted by phone every 2 months until withdrawal of consent, death, or closure of the study by the Sponsor to collect the drug name of any new systemic antineoplastic therapy or the date of death.

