#### 10.5.3.2.2 Overall Survival

Overall survival is defined as the time from date of randomization to death due to any cause. The primary treatment comparison will be based on a rank preserving structural failure time (RPSFT) model to account for treatment crossover effects from regorafenib to avapritinib. The survival time gained/lost by receiving avapritinib after crossover in the regorafenib group will be estimated. Rank preserving structural failure time reconstructs the survival duration of patients as if they had never received avapritinib, assuming treatment is acting by multiplying survival time by a given factor once a patient starts receiving avapritinib ([Korhonen et al, 2012](#)).

If the patient is alive or the vital status is unknown at the time of analysis, OS will be censored at the date the patient is last known to be alive. The Kaplan-Meier method will be used to estimate the distribution of OS for each treatment group. The HR and its 95% CI will be estimated based on Cox's regression model with stratification factors as covariates.

In addition, the probability of survival by time after randomization based on Kaplan-Meier estimates will be tabulated for each treatment group along with the standard errors estimated by the Greenwood formula.

A gate-keeping method will be implemented to control Type I error. The OS will be analyzed when superiority is demonstrated for both PFS and ORR. The OS will also be analyzed at the follow-up when 264 events (deaths) occur.

A sensitivity analysis will be conducted in the ITT population where treatment crossover is ignored. Other sensitivity analyses may be considered as appropriate.

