#### *4.6.3.2 Overall Survival*

Overall survival is defined as the time from randomization to the date of death. Patients who die before or on the data cutoff date will be considered to have had an OS event. All patients who do not have a death record prior to or on the cutoff date will be censored at the last date known alive.

The primary treatment comparison will be based on a stratified log-rank test using the ITT Population. The HR and its 95% CI will be estimated using a stratified Cox model with treatment as the explanatory variable and strata as the stratification factors. An unstratified log-rank test will be performed as a sensitivity analysis.

A rank preserving structural failure time (RPSFT) model will be applied as a supportive analysis to account for treatment crossover effects from regorafenib to avapritinib. The survival time gained/lost by receiving avapritinib after crossover in the regorafenib group will be estimated. The RPSFT reconstructs the survival duration of crossover patients as if they had never received avapritinib, assuming treatment acts by multiplying survival time by a given factor once a patient starts receiving avapritinib (Korhonen et al, 2012). See Appendix 2 (Section 7.4) for further details of implementing this method.

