**7.1.4 Death Date Imputation**

- If death date is completely missing, will use latest alive date + 1
- If both month and day are missing, then use the first date (01 JAN) of the year, or latest alive date + 1, whichever is later
- If only day is missing, then use the first day of the month, or latest alive date + 1, whichever is later.

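### The SAP lets any dated patient record fix the last date known alive, so OS censoring (and possibly imputed death dates) can be too late, though never too early

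*SAP*

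**What the plan says.** Protocol 10.5.3.2.2 states that, for a patient who is alive or whose vital status is unknown at the analysis, "OS will be censored at the date the patient is last known to be alive". It gives no method for finding that date.

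SAP 3.2.6 supplies one. It treats last contact and last date known alive as the same quantity, which "is defined as the last non-imputed date of any patient record" in the clinical database, up to the cutoff. The only limits are that the date is not imputed and does not fall after the cutoff.

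SAP 4.6.3.2 then applies it to OS: "All patients who do not have a death record prior to or on the cutoff date will be censored at the last date known alive".

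SAP 7.1.4 imputes death dates from a latest alive date. For a wholly missing date: "If death date is completely missing, will use latest alive date + 1". For a missing day: "If only day is missing, then use the first day of the month, or latest alive date + 1, whichever is later". The section does not refer to 3.2.6.

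SAP 7.1 adds a general requirement that imputed dates make sense, and gives it precedence over the specific imputation rules. SAP section 6 records no departure from the protocol's analyses.

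**The concern.** The protocol's rule asks for evidence of life; the SAP's definition asks only for a date on a record. The documents describe several kinds of record that need not show the patient was alive:

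- protocol deviations entered in the study database by site staff (SAP 3.6);
- study discontinuation for loss to follow-up, administrative reasons or sponsor decision (SAP 4.2);
- survival follow-up, in which "patients or their designated care giver will be contacted by phone every 2 months" (Protocol 7.9), partly to collect the date of death. A call to a caregiver can end without establishing vital status, or can report a death.

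No section excludes the dates of such records.

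If one of them is a patient's last record, the patient stays in the OS risk set for a period in which no death could have been observed. That lowers the estimated hazard in that patient's arm. OS is a key secondary endpoint under the gate-keeping scheme, with an interim and a final look (SAP 4.6.1). The planned supportive analyses would not expose the problem: the unstratified log-rank test uses the same censoring dates, and the rank-preserving structural failure time analysis starts from the same observed survival times.

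**Working it through.** **1. The plan's own OS figure.** Inputs from SAP 1.3: HR 0.67, two-sided alpha 0.05, 90% power, 1:1 allocation. Schoenfeld's formula gives 4 × (1.960 + 1.282)² / (ln 0.67)² = 42.03 / 0.1604 ≈ 262.1, so 263 deaths against 264 stated. Power at 264 deaths is 90.2%. The plan's figure reproduces, and a date definition does not alter it.

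**2. Direction.** Let A be the set of all non-imputed dated records up to the cutoff, and B the subset that shows the patient alive. Because B lies within A, max(A) ≥ max(B). Compared with the same rule confined to records showing life, the SAP date is either equal or later.

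**3. Imputed deaths, if 7.1.4 uses the 3.2.6 date.** Suppose a caregiver reports on 5 July a death in June, day unknown, and that call is the last record. The rule takes the later of 1 June and 5 July + 1, which is 6 July. That is after the report and outside the known month. If the death date is wholly missing, the rule gives the day after the last record of any kind, and there is no known month against which to test it.

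**4. Size.** If late censoring adds a fraction e of person-time to an arm, the hazard ratio is multiplied by roughly (1 + e for regorafenib) / (1 + e for avapritinib). Similar fractions cancel, so only a difference between arms matters.

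This was checked by simulating 600 trials per scenario. From the documents: 460 patients at 1:1, 18-month truncated exponential accrual with parameter -9, HR 0.67, analysis at 264 deaths, and control median OS of 12 months (Protocol 1.4 gives about 1 year). Assumed, because the documents do not give them: exponential survival, the fraction lost, a mean of 6 months to last evidence of life among lost patients, and a lag of 2 or 6 months from that evidence to the last record. The lag was applied to every lost patient and capped at the cutoff. The Cox model was unstratified.

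| Lost, avapritinib / regorafenib | Lag (months) | HR, correct censoring | HR, late censoring | Rise in median OS, avapritinib / regorafenib (months) |
|---|---|---|---|---|
| 2% / 2% | 2 | 0.680 | 0.680 | 0.0 / 0.0 |
| 2% / 2% | 6 | 0.682 | 0.682 | 0.1 / 0.1 |
| 10% / 10% | 2 | 0.676 | 0.677 | 0.2 / 0.2 |
| 10% / 10% | 6 | 0.675 | 0.676 | 0.7 / 0.6 |
| 20% / 20% | 2 | 0.676 | 0.676 | 0.4 / 0.4 |
| 20% / 20% | 6 | 0.680 | 0.682 | 1.4 / 1.2 |
| 5% / 15% | 2 | 0.673 | 0.682 | 0.1 / 0.3 |
| 5% / 15% | 6 | 0.675 | 0.703 | 0.3 / 0.9 |
| 10% / 20% | 2 | 0.676 | 0.686 | 0.2 / 0.4 |
| 10% / 20% | 6 | 0.672 | 0.701 | 0.7 / 1.2 |
| 15% / 5% | 2 | 0.674 | 0.666 | 0.3 / 0.1 |
| 15% / 5% | 6 | 0.675 | 0.651 | 1.0 / 0.3 |

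The largest shifts in each direction are ratios of 0.701 / 0.672 = 1.043 and 0.651 / 0.675 = 0.964.

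**The case against.** The case against is substantial, and much of it stands.

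- **The SAP makes the protocol's phrase operational rather than rejecting it.** Both terms in 3.2.6 signal that evidence of life is intended, and a careful programmer might restrict the records. That is fair as to intent, but the written rule names any patient record and gives no basis for dropping one.
- **Most censored patients would be unaffected.** For a patient in active follow-up the last record will usually be a visit, scan, dose or survival contact. This stands: the error can occur, but the documents do not show that it does.
- **Which dates the database holds is not shown.** A reader might infer that central radiology read dates or laboratory result dates would count. The documents do not place either in the clinical database, and central reads are made by an external contractor (Protocol 7.5.2). The point does not rest on them. Nor do SAP 3.6 and 4.2 say which dates the deviation and discontinuation records carry.
- **The link to 7.1.4 is an inference.** That section does not cite 3.2.6, and its wording, read plainly, refers to a living patient. For partial dates the default is the first of the month or year, so a later record is also needed. The general rule in SAP 7.1 bears on the July example. It is only a partial guard: it sets no vital-status test and does not reach censoring dates.
- **The visible effects need assumptions.** Long lags also sit poorly with contact every 2 months in both arms; a 6-month lag corresponds to about three contact intervals. This stands, and is why the severity is low.

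**Conclusion.** The definition in SAP 3.2.6 is wider than the protocol's rule for OS censoring, and the resulting error is zero or late. Imputed death dates share the problem only if the alive date in 7.1.4 is the 3.2.6 date.

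The hazard ratio is unchanged to three decimals at the planned 2% dropout and moves by at most about 0.002 with equal loss of up to 20% per arm. With an assumed 10-point imbalance and a lag of 2 to 6 months on every lost patient, it moves by about 0.01 to 0.03. Kaplan-Meier medians can rise even when loss is equal, by 0.4 to 1.4 months at 20% lost per arm.

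A reader might infer that the OS comparison is biased in favor of avapritinib. The documents do not support that. They do not say which arm would lose more patients: more loss on regorafenib moves the hazard ratio toward 1, and more loss on avapritinib moves it away. The 264-death requirement and the 90% power stand. This is a low-severity correction.

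**What to change.** In SAP 3.2.6, define the last date known alive as the latest non-imputed date, on or before the cutoff, of a record that shows the patient alive: an attended visit, an assessment, sample collection, scan acquisition, dosing, questionnaire completion, or a survival contact recorded as alive. State that disposition-form, protocol-deviation, data-entry and death-report dates do not count. If last contact is needed for other purposes, define it separately.

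Use the same defined term in 4.6.3.2 and 7.1.4, with a cross-reference to 3.2.6, so that an imputed death cannot be placed after the contact that reported it.

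The cost is a few lines of SAP wording and a list of qualifying record types for the programmers. No design figure changes. It is best done before the study team is unblinded at the final database lock.
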